### 3. ANALYSIS SETS

Data for all subjects will be assessed to determine if subjects meet the criteria for inclusion in each analysis population prior to unblinding and releasing the database.

**Table 3: Populations for Analyses**

Analysis Set	Definition
Enrolled	All subjects who have signed informed consent.
Randomized	All subjects who are assigned a randomization number in the randomization system.
Safety Analysis Set	All subjects who received a trial vaccination with either ABNCoV2 or Comirnaty.
Immunogenicity Analysis Set (IAS) a	All subjects who are in the Safety Analysis Set, have at least a baseline and 1 post-vaccination neutralizing antibody result, and have neither intercurrent events indicative of SARS-CoV-2 infection nor received a booster for SARS-CoV-2 outside of the trial within 2 weeks of vaccination. If further protocol deviations are found that would have a significant impact on a subject's humoral responses to trial vaccination, decisions on removing these subjects from the IAS will be made prior to locking the database and unblinding for the primary analysis.
Kinetics Analysis Set – 3 Months a	Subset of Part A subjects in the IAS who have neutralizing antibody results for the SARS-CoV-2 index virus at the Week 13 visit (91-105 days after vaccination) and have neither had a SARS-CoV-2 infection by Week 13 nor received a booster for SARS-CoV-2 outside of the trial by Week 13.
Kinetics Analysis Set – 6 Months a	Subset of Part A subjects in the IAS who have neutralizing antibody results for the SARS-CoV-2 index virus at the Week 26 visit (182-196 days after vaccination) and have neither had a SARS-CoV-2 infection by Week 26 nor received a booster for SARS-CoV-2 outside of the trial by Week 26.

aSARS-CoV-2 infection for IAS and the kinetics analysis sets will be determined by subject-reported adverse events of SARS-CoV-2 infection, positive PCR testing, or an increase in nucleocapsid protein indicating COVID-19 infection.

In general, immunogenicity analyses will be performed using the IAS according to the vaccine to which the subject was assigned (ABNCoV2 or Comirnaty by randomization for Part A, ABNCoV2 for Part B). In Part A, subgroup analyses performed within randomization strata will be analyzed according to the randomization stratum the subject reported at the time of randomization, even if upon further review it is determined to be different than the actual grouping to which the subject should have been assigned. This is most likely the case for prior vaccination stratum in Part A. In case the difference between the derived randomization stratum and as-randomized stratum is different for >5% of subjects in Part A, an analysis will be performed using the stratum “as-derived” from the prior COVID-19 vaccination history data.

Because SARS-CoV-2 infection or receipt of an additional SARS-CoV-2 boost vaccine outside of the trial would affect immunogenicity results, kinetic analyses of immunogenicity at Week 13/Month 3 and Week 26/Month 6 will be based on a subset of subjects who have not been naturally infected or received additional boost vaccinations prior to the time point of interest. In addition, to ensure the same population is followed over time, only subjects who have results for

Week 13 or Week 26, respectively, will be included in these analyses. If the number of subjects eligible for the Kinetics Analysis Sets is more than the pre-specified sample size, subjects will be selected randomly.

All safety analyses will be performed on the Safety Analysis Set, and subjects will be summarized based on the vaccine actually received.

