12.6 Primary Analysis

12.6.1 Primary Estimand

The primary variable of interest is the subjects' neutralizing antibody titers against the SARS-CoV-2 index virus measured at 2 weeks after trial vaccination in each Part A cohort, and the variable will be summarized as the ratio of GMTs for ABNCoV2 compared to Comirnaty in subjects meeting the immunogenicity analysis set definition.

The planned primary analysis will be conducted in each of the Part A cohorts, and the null hypothesis of inferiority will be rejected if the ratio of GMTs is within the non-inferiority margin of 0.67, i.e., the lower limit of the 2-sided 97.5% CI of the GMT ratio is \geq 0.67.

ABNCoV2		Clinical Trial Protocol
ABNCoV2-03	Edition 8.0	

The following are considered intercurrent events:

- 1) A positive test for SARS-CoV-2 infection prior to Visit 3 (12 to 16 days after vaccination), by PCR and
- 2) Discontinuation from the trial due to AEs.

For the primary estimand, the second intercurrent event is not considered as having an impact on the SARS-CoV-2 neutralizing antibody levels and therefore the "treatment policy" strategy will be used. Exposure to the virus can have significant effect on SARS-CoV-2 neutralizing antibody levels, and thus subjects who develop intercurrent infections will be excluded from the primary analysis. This is equivalent to the "while on treatment" strategy. Prior to database lock, a data review meeting will determine if any other intercurrent events (e.g., protocol violations) would affect the primary immunogenicity outcome and should result in exclusion of data points from the primary analysis. Strategies to handle these additional intercurrent events will be determined in a blinded fashion.

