12.6.3 Sensitivity and Supportive Analyses

The primary analysis will be supported by descriptive summaries (GMT, their 95% CIs and the median) for each time point (pre- and post-vaccination). Besides summarizing data by cohort, summaries and the 95% CI will also be presented for combined Part A Cohorts 1 and 2.

The proportion of subjects with \geq 2-fold and \geq 4-fold increase in neutralizing antibody titers to the SARS-CoV-2 index virus from baseline to 2 weeks after trial vaccination will be summarized using frequencies and percentages within cohort and arm.

ABNCoV2		Clinical Trial Protocol
ABNCoV2-03	Edition 8.0	

Nucleocapsid protein test results will be used to perform additional sensitivity analyses of the primary endpoint. Test results that are indicative of SARS-CoV-2 infection will be used to exclude subjects from the analysis population as potential additional subjects experiencing the intercurrent event of COVID-19 infection prior to the 2 week timepoint.

Since the window between vaccination and the primary endpoint measurement is short, the number of subjects with missing data is expected to be small. If there are any, missing data will be imputed using a multiple imputation method as a sensitivity analysis for subjects who meet the Safety Analysis Set definition.

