12.8 Exploratory Endpoints

Geometric mean titers of neutralizing antibodies against the SARS-CoV-2 index virus and VOCs, along with their corresponding 95% CIs, will be summarized by time point and cohort for Part A to explore the kinetics of humoral responses over time. Like for the primary analysis, COVID-19 infection is an intercurrent event for analyses of later time points due to its effect on humoral responses. Subjects with evidence of infection after the 2 week peak time point therefore will be removed from the Immunogenicity Analysis Set for these exploratory kinetic analyses. That is, not only will subjects with AEs of COVID-19 and positive PCR tests be removed, but additionally, due to the longer duration between follow-up visits and the possibility of asymptomatic COVID-19 infections, nucleocapsid protein testing will be used to remove subjects who have evidence of COVID-19 infection. Results will be presented in both tabular and graphical format.

ABNCoV2-03

Edition 8.0

Total antibody titers measured by ELISA in subsets of the Part A cohorts and cellular immune responses measured by ELISpot in the immunogenicity subsets of the Part B cohorts will also be summarized using geometric means and their 95% CIs. The difference between the ABNCoV2 and Comirnaty vaccination groups in the Part A cohorts with respect to total antibody titers will also be described by the ratio of their GMTs (ABNCoV2 vs. Comirnaty) and corresponding 95% CIs within each cohort. All analyses will be considered descriptive. The GMTs and 95% CIs will also be plotted as a function of time for each assay and vaccination group for the applicable parts and cohorts on the log₁₀ scale.

Fold increases, defined as post-baseline titers divided by the baseline titers, will be summarized by assay, vaccination group (if applicable), and timepoint within each part and cohort. They will further be summarized by subgroups (age, baseline titer category, baseline comorbidity, previous vaccination regimen, history of known SARS-CoV-2 infection, and time from previous vaccination). Similar to the titers, fold increases will also be summarized by geometric means and corresponding 95% CIs.

The combined cohort analyses for Part A will be similar to the analyses performed for each cohort.

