### Primary Estimand

The primary variable of interest is the subjects' neutralizing antibody result against the SARS-CoV-2 index virus measured at 2 weeks after trial vaccination in each Part A cohort, and the variable will be summarized as the ratio of geometric means for ABNCoV2 compared to Comirnaty in subjects meeting the Immunogenicity Analysis Set (IAS) definition.

The planned primary analysis will be conducted in each of the Part A cohorts, and the null hypothesis of inferiority will be rejected if the ratio of GMTs is within the non-inferiority margin of 0.67, i.e., the lower limit of the 2-sided 97.5% CI of the GMT ratio is  $\geq 0.67$ .

The following are considered intercurrent events:

1. Development of COVID-19 symptoms and having a positive test for SARS-CoV-2 infection prior to Visit 3 (12 to 16 days after vaccination) by PCR or other testing method,

2. Administration of a booster for SARS-CoV-2 prior to Visit 3, and
3. Discontinuation from the trial due to AEs.

For the primary estimand, the third intercurrent event is not considered as having an impact on the SARS-CoV-2 neutralizing antibody levels and therefore the “treatment policy” strategy will be used. Exposure to the virus or receiving another booster vaccine can have significant effect on SARS-CoV-2 neutralizing antibody levels, and thus subjects who develop intercurrent infections will be excluded from the primary analysis. This is equivalent to the “while on treatment” strategy. Prior to database lock, a data review meeting will determine if any other intercurrent events (e.g., protocol violations) would affect the primary immunogenicity outcome. Strategies to handle these additional intercurrent events will be determined in a blinded fashion.

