### 4.2.3. Sensitivity Analyses

All results excluded from the primary estimand analysis will be included with the sensitivity analysis for a full account of the trial population, i.e., the safety analysis set. Reasons for exclusion may include, but are not limited to:

- Intercurrent events indicative of SARS-CoV-2 infection prior to 2 weeks after vaccination
- A protocol deviation substantially affecting the immunogenicity outcome (i.e., exclusion from the Immunogenicity Analysis Set)

Another sensitive analysis will further exclude subjects who have significant fold increase in nucleocapsid protein antibody results although neither have positive PCR nor SARS-CoV-2 infection reported as an adverse event.

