##### 4.5.6.2. SARS-CoV-2 Infection Results via Nucleocapsid Protein Testing

Nucleocapsid protein IgG results will be listed. The results will support a sensitivity analysis of the primary immunogenicity endpoint excluding subjects with an increase in nucleocapsid protein IgG levels potentially indicative of a natural SARS-CoV-2 infection prior to the immunogenicity testing visit.

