#### **4.8. Changes to Protocol-planned Analyses**

##### Nucleocapsid Protein IgG Testing

A change from the protocol on the use of the nucleocapsid antibody testing to define intercurrent events for the primary estimand has been incorporated into this SAP. The intercurrent event of COVID-19 infection, and use of the “while on treatment” strategy, is only intended to exclude the significant effects an infection would have on the immunogenicity response for a subject. The antibody response to the trial vaccine could not be distinguished from the antibody response to a SARS-CoV-2 infection in this situation. As no current vaccines contain the nucleocapsid protein, the nucleocapsid IgG test was added to ensure subjects with recent infections were not included in the analyses.

Nucleocapsid protein IgG testing results in a study of the kinetics of these antibodies after SARS-CoV-2 infection show the average peak occurred 72 days after a positive PCR test result,

and a 90.8% sensitivity in samples collected >14 days after the start of symptoms (Loesche, 2022). This suggests that subjects who had SARS-CoV-2 infection prior to baseline may continue to have increases in antibody levels against the nucleocapsid protein during the 2-week period from baseline to the primary endpoint time point. On the other hand, subjects who had new infection after baseline may not have significant increases during the short period of time. Thus, the nucleocapsid protein antibody results are not a good indicator for natural infection acquired between baseline and Week 2.

The risk of missing natural COVID-19 infections by not accounting for nucleocapsid IgG test results is low. Subjects are required to test negative for COVID-19 at screening via PCR test. Additionally, those attending the Week 1 or Week 2 visits with clinically relevant symptoms are tested by PCR for infection, such that concurrent infections during the 2 week period should be captured either by PCR test or adverse event reporting.

The risk of excluding subjects who had older infections that may have occurred prior to baseline is not negligible due to the kinetics of the nucleoprotein protein IgG test. Therefore, in the interest of having a more inclusive primary analysis it has been decided to remove the nucleocapsid protein IgG testing from the intercurrent event of COVID-19 infection and retain the results for a sensitivity analysis.

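### SAP Table 3 footnote a removes subjects with a nucleocapsid rise from the primary analysis set, which SAP 4.8 decided against; the infection and baseline rules for that set also conflict

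*SAP*

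**What the plan says.** **Nucleocapsid.** SAP Table 3 excludes from the IAS anyone with an infection event within 2 weeks of vaccination. Its footnote a, attached to the IAS and to both Kinetics Analysis Sets, establishes infection from reported adverse events of "SARS-CoV-2 infection, positive PCR testing, or an increase in nucleocapsid protein indicating COVID-19 infection". SAP 4.2.2 estimates the primary estimand in the IAS. SAP 4.8 then records that "it has been decided to remove the nucleocapsid protein IgG testing from the intercurrent event of COVID-19 infection". SAP 4.2.3 accordingly plans: "Another sensitive analysis will further exclude subjects who have significant fold increase in nucleocapsid protein antibody results", limited to subjects with neither a positive PCR nor an infection adverse event; 4.3.1.3 repeats this for the variants. SAP 4.5.6.2 says: "The results will support a sensitivity analysis of the primary immunogenicity endpoint excluding subjects with an increase in nucleocapsid protein IgG levels". Protocol 12.6.3 has the same role for the test: "Nucleocapsid protein test results will be used to perform additional sensitivity analyses of the primary endpoint". Protocol 12.8 goes further only for the later kinetic analyses, where "nucleocapsid protein testing will be used to remove subjects who have evidence of COVID-19 infection".

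**Infection rule.** SAP 1.1 defines the intercurrent event as "Development of COVID-19 symptoms and having a positive test for SARS-CoV-2 infection prior to Visit 3", by PCR or another method. Protocol 12.6.1 has "A positive test for SARS-CoV-2 infection prior to Visit 3 (12 to 16 days after vaccination), by PCR", with no symptom condition.

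**Baseline titer.** SAP Table 3 and Protocol 12.5 require a baseline neutralizing result for the IAS. SAP 4.1.4 keeps subjects without one, reasoning that the primary analysis does not need it. The model in SAP 4.2.2 has baseline titer as a covariate.

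**The concern.** Table 3 is the formal definition from which a programmer would build the set. SAP 2.1 states that only Cohort 2 will be formally tested, so the confirmatory result rests on this one set.

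SAP 4.8 gives a reason for its decision: nucleocapsid antibody may still be rising after an infection that preceded baseline, and may not yet have risen after a new one. Footnote a removes exactly the subjects that argument was meant to protect. It also weakens the check on them, because the sensitivity analysis that should exclude them has few or none left to exclude.

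The other two conflicts matter less but concern the same set. An asymptomatic PCR-positive subject is in or out depending on the section read. A subject without a baseline titer counts towards the IAS under 4.1.4 but cannot enter the covariate model.

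**Working it through.** **Step 1: who is excluded under each rule.** Three kinds of subject, with the event before Visit 3:

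| Subject | SAP 1.1 | Protocol 12.6.1 | SAP Table 3, footnote a |
|---|---|---|---|
| Nucleocapsid rise only; no symptoms, PCR or AE | kept | kept | removed |
| Positive PCR, no symptoms | kept | removed | removed |
| Symptoms, positive by a test other than PCR, reported as an AE | removed | kept | removed |

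No two columns agree. SAP 4.8 sides with the first two columns on the first row. It does not declare the symptom condition as a departure from the protocol.

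**Step 2: the nucleocapsid sensitivity analysis.** SAP 4.2.3 targets subjects with a rise but no positive PCR and no infection AE. That is the first row, which footnote a has already removed. Any difference left depends on how an increase (Table 3) differs from a significant fold increase (4.2.3). Neither is defined.

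**Step 3: baseline.** A complete-case model with baseline as covariate uses the same subjects under either rule. What changes is the IAS count and the descriptive GMTs. The count against the 400 minimum may also change, because Protocol 5.1 counts subjects with primary endpoint data, and a subject without baseline can have those.

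**Step 4: the plan's power figures.** Inputs from SAP 5.1: SD 0.52 on the log10 scale, margin 0.67, one-sided alpha 0.0125, 450 evaluable (minimum 400). Allocation is 1:1. A true GMT ratio of 1 is assumed, because the documents do not state it.

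Power = Φ( −log10(0.67) / (0.52 × √(2/n)) − z(0.9875) ), where n = N/2 per arm, −log10(0.67) = 0.1739 and z(0.9875) = 2.241.

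- N = 450: 0.1739 / (0.52 × √(2/225)) = 3.548; 3.548 − 2.241 = 1.306; power 0.904. The plan says about 90%.
- N = 400: 0.1739 / (0.52 × √(2/200)) = 3.345; 3.345 − 2.241 = 1.103; power 0.865. The plan says about 86%.

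Both reproduce; the noncentral t gives 0.903 and 0.863.

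**Step 5: effect of footnote a on power.** The documents give neither a rate of nucleocapsid rise nor the Cohort 2 evaluable count, so this is an assumed range starting from 450:

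| Removed | Left | Power |
|---|---|---|
| 1% | 445.5 | 0.901 |
| 2% | 441 | 0.898 |
| 5% | 427.5 | 0.888 |
| 10% | 405 | 0.870 |

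To fall below the 400 minimum, more than 450 − 400 = 50 subjects would have to be removed, or 50/450 = 11.1%.

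**The case against.** **Version order.** SAP 1.0 is dated 19 May 2023 and based on Protocol Edition 7; Edition 8 is dated 30 June 2023. The SAP could not follow a later edition. This is fair for the comparison with Edition 8 and for the SAP's visit schedule. It does not touch the conflict between footnote a and 4.8, which lies inside one approved SAP.

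**Intent is recoverable.** Sections 4.2.3, 4.3.1.3, 4.5.6.2 and 4.8 all point the same way, and membership of the set is settled blinded before lock. That limits the risk, but footnote a remains the formal definition.

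**Robustness is tested elsewhere.** The first sensitivity analysis in 4.2.3 uses the Safety Analysis Set and brings excluded results back. It does so for all exclusions together, however, and cannot isolate the nucleocapsid group.

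**The infection rules differ little in practice.** Post-vaccination PCR is done only when clinically indicated, so most PCR-positive subjects will have symptoms. A PCR-or-AE rule is visible in 4.2.3, 4.3.1.3 and 4.8, and Protocol 12.5 excludes positive tests without limiting them to PCR. This stands: the symptom condition in SAP 1.1 is the real outlier, and few subjects are likely to be affected.

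**Few rises and few missing baselines are likely.** COVID-19 within 3 months and a positive screening test are exclusions, so pre-baseline infections would mainly be unrecognised ones, and the pre-vaccination Visit 1 sample is mandatory. Both points are reasonable, and no bias in the GMT ratio has been shown.

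**Conclusion.** The concern holds, and footnote a is wrong as written. Applied to the IAS, it reverses the decision in SAP 4.8 and leaves the nucleocapsid sensitivity analysis largely a repeat of the primary analysis. The infection-rule and baseline conflicts are also real, but smaller.

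The numerical effect is probably modest. With a true ratio of 1 and SD 0.52, removing up to 10% of 450 keeps power at about 0.87 or higher, above the roughly 86% the plan accepts at 400. Only a loss of more than 11.1% would make the cohort's result descriptive. These percentages are illustrative. The main consequence is that the population for the only formally tested cohort is not uniquely defined. This should be fixed before unblinding; it does not threaten the design.

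**What to change.** - **Footnote a:** limit the nucleocapsid clause to the two Kinetics Analysis Sets, as in Protocol 12.8.
- **SAP Appendix 1, footnote i:** replace testing at V1 and V3 only with V1, V3, FU2 and FU3, as in Protocol Edition 8 section 1.4. Otherwise the Week 13 and Week 26 sets rest on the same V1-to-V3 change that 4.8 distrusts.
- **Infection rule:** use one rule for the IAS in SAP 1.1 and Table 3. Either follow Protocol 12.6.1 (positive PCR before Visit 3), or declare in 4.8 any difference, such as adding COVID-19 adverse events or requiring symptoms.
- **Baseline:** delete the second paragraph of SAP 4.1.4, so that the IAS requires a baseline titer as in Table 3, Protocol 12.5 and the model.
- **Nucleocapsid rise:** define it once, with an assay-based criterion fixed before unblinding, and use it in both the sensitivity analyses and the kinetics sets.

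The cost is SAP wording only. No new data are needed, because the FU2 and FU3 nucleocapsid tests are already in Protocol Edition 8.

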## 4. STATISTICAL ANALYSES

### 4.1. General Considerations

All individual data entered in the electronic case report form (eCRF) will be listed as recorded in subject-level data listings. Listings will be sorted by trial part (A or B), Cohort (1 or 2), vaccination arm (for Part A), subject, time point, and parameter (if applicable), based on the domain presented. Tables and figures for Part A will be created separately from Part B tables.

Descriptive statistics presented for categorical variables will include frequencies and percentages (i.e., n (%)), with the denominator for the percentage calculation defined in the table. Unless otherwise stated, descriptive statistics presented for continuous variables will be n, mean, median, standard deviation, minimum, and maximum.

In general, all tables and figures will be presented by cohort (Cohort 1, Cohort 2, Cohort 1+2). For Part A, tables will also be presented by vaccination arm (ABNCoV2 versus Comirnaty) within each cohort. For subject population summaries including disposition and demographics, an “Overall” column will be presented for the combined Cohort 1+2 grouping.

Unsolicited AEs will be summarized at both the event and subject level, with percentages based on subject counts. As solicited AEs can only be experienced once per event type per subject, only subject level counts and percentages will be presented.

All statistical summaries and analyses will be performed using SAS® version 9.4 or higher (SAS Institute, Cary, NC, USA).

